3.7.4 Interventions

When there are changes in specific clinical characteristics of the patients, a notification will be created. The doctor will be informed for these notifications of the Test group through the RETENTION platform. After a notification pops-up, the doctor should contact the patient to confirm the parameters, check the factors that

may lead to the changes (e.g., salt intake, non-adherence to medical therapy), manage the clinical situation -if possible- remotely (e.g., Increase diuretic, adjust beta-blocker dose) or arrange an unscheduled visit if needed.

Clinical characteristics	Type of Notification	Definition of Notification	Type of Intervention	Clinical Intervention
Weight:	Low level:	Gain >2kg in one day or gain > 3 Kg in seven days	1. Dismiss notification-measurement error-not clinically relevant2. Telephone visit3. Schedule in-personvisit	- Reinforce dietetic plan - Increase diuretic dose
	Critical level:	Gain ≥3kg in 2 days	 1. Dismiss notification -measurement error -not clinically relevant 2. Telephone visit 3. Schedule in-person visit 	- Reinforce dietetic plan - Increase diuretic dose - Check if IV diuretic is needed - Consider visiting the emergency department (ED)
Blood pressure:	Low level:	Systolic Blood Pressure (SBP) < 100 mmHg and a 10 mmHg reduction from the average of the previous 3 measurements) or SBP>140mmHg	 Dismiss notification -measurement error -not clinically relevant 2. Telephone visit 3. Schedule in-person visit 	-Check for triggers: Temperature, hypovolemia -Check if Hypovolemia (sweat, diarrhoea) -Consider reducing dose of diuretics, ARBs, B- blockers, MRAs, ARNIs etc
	Critical level:	Systolic Blood Pressure (SBP)< 90 mmHg and a 10 mmHg reduction from the average of the previous 3 measurements mmHg or SBP>150mmHg	-1. Dismiss notification -measurement error -not clinically relevant 2. Telephone visit 3. Schedule in-person visit	-Check for triggers: Temperature, hypovolemia -Check Temperature -Check if Hypovolemia (sweat, diarrhoea) -Consider adjust dose of ARBs, B-blockers, MRAs,ARNIsetc -Consider visiting the emergency department (ED)
Heart Rate:	Low level:	<50bpm or >110bpm and 10 bpm change from the average of the	1. Dismiss notification -measurement error -not clinically relevant	-Check for triggers: Temperature, hypovolemia

Table 3: Cut-off values for notifications and interventions in the RETENTION grou	a
	· •

		3 previous	2. Telephone visit	-Check Temperature
		measurements	3. Schedule in-person	-Check if Hypovolemia
			visit	(sweat, diarrhoea) -Consider adjust dose of antiarrhythmic drugs (B- blockers, digoxin) -Check symptoms (dizziness, palpitations)
	Critical level:	<40 bpm or >150bpm	1. Dismiss notification -measurement error -not clinically relevant 2. Telephone visit 3. Schedule in-person visit	-Check for triggers: Temperature, hypovolemia -Check Temperature -Check if Hypovolemia (sweat, diarrhoea) -Consider adjust dose of antiarrhythmic drugs (B- blockers, digoxin) -Check symptoms (dizziness, palpitations) -Consider visiting ED
Peripheral capillary oxygen saturation:	Low level:	<95% and a 2% reduction from the average of the 3 previous measurements	1. Dismiss notification -measurement error -not clinically relevant 2. Telephone visit 3. Schedule in-person visit	-Check for dyspnoea, oedema, cough or other symptoms -Check temperature -Advice to monitor promptly
	Critical level:	<90%	1. Dismiss notification-measurement error-not clinically relevant2. Telephone visit3. Schedule in-personvisit	-Consider visiting ED- Advice medical evaluation
Temperature:	Low level:	>37,2 ∘C	1.Dismiss notification -measurement error -not clinically relevant 2. Telephone visit 3. Schedule in-person visit	-Check for LVAD driveline exit -Other symptoms
	Critical level:	>37,8 °C	1. Dismiss notification -measurement error -not clinically relevant	-Check for LVAD driveline exit -Other symptoms

			2. Telephone visit	-Consider take
			3. Schedule in-person visit	antipyretics/antibiotics
Symptoms:	Low level: Critical level:	1 day of deterioration More than 3 days of deterioration	1. Dismiss notification -measurement error -not clinically relevant 2. Telephone visit 3. Schedule in-person visit 1. Dismiss notification -measurement error	-Re-evaluate -Consider adjustment of medical therapy -Consider visiting ED
			-not clinically relevant 2. Telephone visit 3. Schedule in-person visit	
Activity:	Low level:	30% weekly decrease in activity	1. Dismiss notification-measurement error-not clinically relevant2. Telephone visit3. Schedule in-personvisit	-Discuss with patient reasons for low activity (symptoms, fatigue, boredom, other reasons) -If not due to change in symptoms, advice to increase activity
	Critical level:	70% weekly decrease in activity	1. Dismiss notification -measurement error -not clinically relevant 2. Telephone visit 3. Schedule in-person visit	-Check symptoms -Consider medical evaluation -Consider specialist advice (depression?)
Sleep:	Low level:	More than 14 days sleeping ≤5 hours	1. Dismiss notification-measurement error-not clinically relevant2. Telephone visit3. Schedule in-personvisit	-Check if it is because of Symptoms? -Inform again the need for a normal sleeping pattern -Consider specialist advice (neurologist- psychologist etc.)
Adherence to treatment		≥ 3 days without treatment adherence	Telephone visit	-Check reasons for non-adherence -Reinforce importance of medication -Schedule an in-person visit

				-Consider ED
Pulsatility index:	Critical Level:	Profound reduction below 2 (<2)	1. Dismiss notification-measurement error-not clinically relevant2. Telephone visit3. Schedule in-personvisit	-Check for Hypovolemia -Consider changing medication
Flow:	Low Level:	Progressive flow reduction every day	1. Dismiss notification -measurement error -not clinically relevant 2.Telephone visit 3.Schedule in-person visit	-Check symptoms -Check hypovolemia/hypertensio n -Consider changing medication (diuretics/ antihypertensive drugs) -Visit VAD clinic
	Critical Level:	Flow below 2.5	 1. Dismiss notification -measurement error -not clinically relevant 2. Telephone visit 3. Schedule in-person visit 	-Check symptoms -Check hypovolemia/hypertensio n -Consider changing medication (diuretics/ antihypertensive drugs)- Visit VAD clinic
Watts:	Critical Level:	Watts above 6	1. Dismiss notification-measurement error-not clinically relevant2. Telephone visit3. Schedule in-personvisit	-Check symptoms -Visit VAD clinic -Check INR levels
Driveline:	Critical Level:	Change in the colour of the driveline	1. Dismiss notification-measurement error-not clinically relevant2. Telephone visit3. Schedule in-personvisit	-Check Temperature -Consider antibiotics -Visit VAD Clinic

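### Table 3, low-level blood pressure: the only drug action for systolic pressure above 140 and up to 150 mmHg is a dose reduction, which is the wrong direction

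*Protocol*

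**What the plan says.** Table 3 in Protocol section 3.7.4 lists, for the test (RPMI) arm, the cut-offs that raise a notification and the clinical response to each. *Low level* and *critical level* are grades of severity, not directions.

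- **Blood pressure, low level.** Trigger: "Systolic Blood Pressure (SBP) < 100 mmHg and a 10 mmHg reduction from the average of the previous 3 measurements) or SBP>140mmHg". The single Clinical Intervention cell asks for checks of temperature and hypovolaemia and then gives one drug action, "Consider reducing dose" of diuretics, ARBs, beta-blockers, MRAs, ARNIs and the like.
- **Blood pressure, critical level.** Trigger: SBP below 90 mmHg with a 10 mmHg "reduction from the average of the previous 3 measurements mmHg or SBP>150mmHg". The drug action is "Consider adjust dose of" ARBs, beta-blockers, MRAs, ARNIs and so on.
- **Lead-in to the table.** The doctor is to contact the patient, confirm the reading, look for contributing factors such as salt intake or non-adherence, and manage remotely if possible. The drug examples given are "e.g., Increase diuretic, adjust beta-blocker dose".

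Sections 3.2.1 and 3.7.5 leave any intervention to the treating physician's judgement, and section 3.7.5 also names the 2021 ESC heart failure guideline.

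**The concern.** The low-level row joins a hypotension trigger and a raised-pressure trigger but gives a response for the first only. Every drug class it names lowers blood pressure or volume. Followed as written, a patient with mildly raised systolic pressure would be considered for less of that treatment. The cell contains no prompt for raised pressure that would offset this.

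The table defines the intervention being tested, across six hospitals in four countries. It should not list a contrary drug action for one of its own triggers. What is at stake is patient safety and a consistent intervention. The sample size and the analysis are not affected.

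**Working it through.** The check is mainly a comparison of table entries, with two small pieces of arithmetic. The protocol states no figure of its own on this point to reproduce.

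**1. The affected band.** The low-level high trigger is SBP >140 mmHg and the critical high trigger is SBP >150 mmHg.

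| SBP (mmHg) | >140? | >150? | Level reached |
|---|---|---|---|
| 140 | no | no | none |
| 141 | yes | no | low only |
| 150 | yes | no | low only |
| 151 | yes | yes | critical |

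Readings above 140 and up to and including 150 mmHg therefore have only the low-level row to go by.

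**2. Trigger direction against dose direction.** These are the six levels in Table 3 for weight, blood pressure and heart rate:

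| Level | Trigger | Dose wording | Consistent? |
|---|---|---|---|
| Weight, low | one-sided: "Gain >2kg in one day or gain > 3 Kg in seven days" | "Increase diuretic dose" | yes |
| Weight, critical | one-sided: gain of 3 kg or more in 2 days | increase diuretic | yes |
| Blood pressure, low | two-sided: <100 with a fall, or >140 | "Consider reducing dose" | **no, for >140** |
| Blood pressure, critical | two-sided: <90 with a fall, or >150 | "Consider adjust dose of" | yes, neutral |
| Heart rate, low | two-sided: <50 or >110 bpm, with a 10 bpm change | "Consider adjust dose of antiarrhythmic drugs (B- blockers, digoxin") | yes, neutral |
| Heart rate, critical | two-sided: <40 or >150 bpm | adjust, same drugs | yes, neutral |

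Four levels have a two-sided trigger, and three of them use neutral wording. Three levels fix a dose direction; the two weight levels are triggered by gains only, so their direction fits. Low-level blood pressure is the only level that combines a two-sided trigger with a fixed dose direction. The LVAD flow rows show the same habit: where the cause may be hypovolaemia or hypertension, they speak of changing medication without giving a direction.

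**3. Whom the row can apply to.** Section 3.7.3 excludes LVAD patients from daily home blood pressure. Section 3.4.1 plans 200 heart failure and 100 transplant patients, with equal arms within each category:

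- test-arm patients with home blood pressure = (200 + 100) / 2 = 150
- share of the test arm = 150 / 225 = 66.7%

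This is coverage, not expected events. The protocol does not say how often a reading falls above 140 and up to 150 mmHg, so no count of notifications is derived.

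**The case against.** The best defence is that the cell is a menu. The reduction line follows the hypovolaemia check, so a cardiologist would read it as the low-pressure pathway and ignore it for a high reading. Table 3 works this way elsewhere: both temperature levels prompt a driveline check although most patients have no driveline. On that reading the row is incomplete rather than wrong. The safeguards are also real. The wording is only to consider, the notification may be dismissed, the lead-in has the reading confirmed and even gives an increased diuretic as an example, and advice rests on clinical judgement and the ESC guideline in centres chosen for experience. The protocol does not say that the Clinical Intervention text is displayed with the notification.

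Most of this stands, and it limits the weight of the point: harm is unlikely. It does not make the row correct. Even read as a menu, the cell offers no suitable drug action for a trigger that the row itself defines. The lead-in examples are general and are not tied to SBP above 140 mmHg.

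Two further objections are fair. The 66.7% measures eligibility, not exposure, and should not be read as the size of a risk. The critical row also lacks a specific prompt for raised pressure, so splitting the low-level row is optional. The necessary correction is the single word.

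**Conclusion.** The point holds as a minor safety wording error. For systolic pressure above 140 and up to 150 mmHg, the only drug action in the applicable row is to reduce blood-pressure-lowering therapy. One of the four two-sided levels in Table 3 is affected, and the row can cover 150 of the 225 test-arm patients. The band assumes that once SBP exceeds 150 mmHg the critical row governs, although the low-level condition is then also met. The coverage figure assumes that recruitment meets its category targets with equal arms. Nothing is claimed about the number of notifications, the primary endpoint, power or the analysis.

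**What to change.** In the low-level blood-pressure row of Table 3, replace *reducing* with *adjusting*, matching the critical row. That is sufficient.

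If the sponsor prefers more guidance, the row can be split. The hypovolaemia checks and dose reduction would stay with low SBP. A high-SBP line would prompt checks of salt intake and non-adherence, which the lead-in already mentions, and adjustment of therapy according to the 2021 ESC guideline. The critical row can stay as it is.

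The cost is a one-word edit or one split row, plus the same edit in any platform text that reproduces the table. No additional patients, visits or staff are needed.

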3.7.5 Receiving Notifications

Patients will be advised that the clinical team will only receive notifications in the RETENTION group, and that the RETENTION is not an alarm system. In case of severe symptoms, the patient will be instructed to contact the emergency services.

Notifications will be created through the RETENTION platform for both study groups, however the clinicians will be informed only for notifications from the intervention group. Once a notification appears on the clinician's interface on the platform, he/she will communicate with the patient to obtain further information regarding patient's clinical condition. If, based on type of notification and information obtained through contact with patient, the notification is considered clinically relevant, the physician will provide specific advice/ instructions to the patient through either remote consultation or by arranging an unscheduled clinic visit with the patient. All consultations and medical instructions/advice will be made by clinicians according to their clinical judgement and based on the 2021 European Society of Cardiology Guidelines for the Diagnosis and Management of Heart Failure.

3.7.6 Study management, study monitoring, data and sample management

Both clinicians and patients / carers will have access to the RETENTION platform under different roles and privileges albeit sharing a secure authentication scheme. On registration to the study, patients and caregivers will also be registered in the RETENTION platform and be given access credentials. Reporting and statistics facilities will be provided. All recruited patients and caregivers will go through the standard education and training regarding their condition, as well as on using the RETENTION platform.

It should also be noted that RETENTION will abide to all principles of GDPR including the principles of lawfulness, fairness and transparency, purpose limitation, and data minimisation. Towards the realisation of these principles, RETENTION has adopted a layered architecture in which non-anonymised personal patient data will only be stored at the components of the platform operating at the clinical sites involved in the clinical study of the project and be accessible only to local clinicians, having responsibility for the follow ups of patients and making appropriate interventions for them. These personal data will be transmitted only in a fully anonymised form to the cloud of the platform for analysis using AI techniques (data mining and machine learning). It should also be noted that any processing operations on non-anonymised personal data held at the clinical sites of the project shall be limited strictly to what is absolutely necessary, e.g., having the minimal reports necessary for authorised clinical personnel to perform their duties for the purposes of the project (e.g., conducting follow ups in the context of a visit and approving suggested interventions or otherwise). And beyond these notes, it should be stressed that any data processing in the RETENTION platform will be done in such way to ensure demonstrable compliance with the GDPR.

Study management, study monitoring, data and sample management will be in line with the regulatory requirements that have been described above in section 3.3. The clinical coordinator of the RETENTION consortium and the principal investigators of the clinical sites will be overseeing the execution and progress of the study, in regular monthly meetings.

3.7.7 Sponsor coordinating centre(s) and committees

The sponsor of the clinical study will be the OCSC. The sponsor will be responsible as per EU regulation (No 536/2014) defines.

3.7.8 Study medication

No additional medications included apart from the already prescribed per patient.

3.7.9 Clinical centres

The clinical sites which will participate in the study are shown in Table 1. These centres were selected on their previous experience on this field and on the number of patients they treat.

3.8 Orphan designation (if needed)

No orphans included.

3.9 "Unit cost per patient" for clinical trial, studies, investigations

RETENTION uses actual costs.

4 Organisational issues

For each Pilot set-up, a set of activities will be carried out in anticipation of study participants, at technical, clinical, and administrative level, that are described in through this section.

- In order for the equipment to be delivered in the time required per study participants' category, the acquisition of complete sets of devices must have been concluded well in advance to the pilot start.
- Each host organisation (Greek Pilot: OCSC and NKUA, German Pilot: UKESSEN, Italian Pilot: UNIBO, Spanish Pilot: SERMAS-HURC and SERMAS-HUPH) associated to a RETENTION pilot, should have designated the team members (registered end-users of the CSB@Dashboard):
 - Clinical team, responsible for the clinical study (i.e., recruitment, clinical protocol adherence, monitoring), including organisational procedures and communication with the participant on medical issues;
 - The head of the clinical study along with his/her communication info will be referred to the accompanying information material of the study that will be handed to each participant.
 - $\circ~$ Technical team, who will handle the initial installation and monitoring of the smooth operation of associated with each patient's devices.
- User guide and troubleshooting instructions will include communication info for providing guidance in cases of technical difficulties or for triggering actions for maintenance/repairing in case of malfunctions.
- Several dissemination activities using the different RETENTION materials (e.g., leaflets, posters, website, social media accounts, etc.) can be used for gathering expressions of interest.
- The start date for the recruitment defined in section 3.

4.1 Phase A: Pre-recruitment

During the pre-recruitment, the Clinical team checks the participants' condition in accordance with the inclusion and exclusion criteria (defined in section 3) and assess their willingness to participate in the RETENTION study. In some cases, additional examinations for participants with a recent history of what could become exclusion criteria can be requested. Those best meeting the requirements and who could benefit from this project through remote monitoring, will be informally approached by the Pilot Clinical team to be informed about the project objectives, the involved activities, their tasks upon participation and the advantages and disadvantages according to their health condition that they could obtain.

Subsequently, those who are willing, without a shadow of a doubt, to participate (and meet the selection criteria) form a list whose members will be later contacted at the start of the recruitment procedures. The list contains personal data (i.e., full names, contact details, other PIIs, desire to participate), and will be under the supervision of the head of the Pilot Clinical team. For those that have met the selection requirements and are keen to participate, still have expressed some doubts or concerns, additional explanations could be provided, and their concerns are collected for future evaluation.

The list containing personal data of potential RETENTION study participants is kept in a safe place. This information is not part of the one collected by the RETENTION platform.

Information will be erased once the pre-recruitment phase is over.

4.2 Phase B: Recruitment

For those who want to participate without a doubt and met selection criteria, complementary diagnostic exams will be held to validate in certainty that they do not meet exclusion criteria relating to recent illness that could compromise their participation in the study, or to reveal a previously unspotted condition (exclusion criteria) making their participation unfeasible. Considering that these initial selections are based on the willingness of each participant that may change until the "Recruitment day" (e.g., loss of interest, significant change in daily life, personal reasons), or the established medical conditions change, participants will be asked again about their interest in participating in the study prior to the baseline assessment. Those who have expressed second thoughts will be placed on a separate play-off list.

The recruitment (procedure that has previously obtained local ethics approval) of each study participant that takes place at the premises of the host organisation (participating to a Pilot), depends on a framework of mandatory activities and ancillary procedures, supported primarily by the Clinical Site Backend (CSB) of the RETENTION platform (CSB@Dashboard), and the required documentation and its evaluation in accordance with the GDPR, namely the paper-based informed consent form (ICF) (in English and in pilot's language, two copies for each edition to be singed) and the Data Protection Impact Assessment (DPIA) (English), along with study-relevant information documents (pilot language), and other material (e.g., informative leaflet in pilot language, end-user guide for the devices to be handed).

The (paper-based) signed informed consent form (ICF) containing personal data of the recruited RETENTION study participant is kept in a safe place. In relation to this, data that later on (all the eligibility conditions are confirmed) will be stored within the CSB are the PseudoID-1 (unique identifier created automatically), home details, contact phone, (1 up to 3) person(s) and contact details who can be notified in case of an emergency, and the date of signature.

The signed ICF is the only element that captures the correlation of the PseudoID-1 and the real identity of the participant.

In case of - for any reason - withdrawal of the consent, the CSB@Dashboard record will capture the new status (withdrawn participant) and date of the withdrawal. From that moment onwards, device/sensor usage data will not be digested.

During the recruitment phase, the baseline assessment (i.e., clinical assessment activities during 1st visit) will be conducted in the context of the host organisation, providing all patients with the necessary safety measurements in agreement with the National/Regional Health Authorities.

The recruitment starts with a phone call (by the Clinical team) scheduling appointment for participants that were previously enlisted in the pre-recruitment list. At the time and date of the appointment, the participant is informed by a member of the Clinical team where additional clarifications for RETENTION project are given. In this moment, the ICF and informative material are presented to the participant (2 copies for each language, for host organisation and participant), but is not signed by him/her yet.

After presenting this information, personal health record information (presented in section 3) is collected and two important questionnaires are applied firstly, since their results can imply exclusion criteria in RETENTION clinical study. It is only after the analysis of the results of these questionnaires and the gathering of information in accordance with the inclusion and exclusion criteria that it is possible to confirm whether the potential participant meets the medical criteria and has the necessary fine motor skills to use the

equipment and devices to be provided by the project. These are important requirements that attest to the capacity of the participant and the benefit of his/her participation in a project of this nature. Once all the eligibility conditions are confirmed, the participant is considered recruited, and then is invited to sign the ICF (signifies the "Recruitment day" timestamp) and begin the baseline assessment (initial RETENTION patient record is about to created, while answers (values) of questionnaires' questions will be inputted as well).

Designated member of the Clinical team (CSB@Dashboard end-user role: Clinician or clinical expert), creates the patient record. It is then when the unique identifier PseudoID-1 for him/her is created. This identifier is entered in the signed ICF.

All members of the Clinical team have access to the full medical record of the recruited study participant (associated to the host organisation).

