3.7.2 Description of recruitment strategy

Candidates for the study are already available from the existing pools of patients available in each of the participating hospitals. The target number of recruited patients for each of the hospitals is shown in Table 1. The recruitment target ratios for the different types of patients will be preserved across the clinical units of each country.

The pool of patients already available will be thoroughly screened based on the last clinical evaluation and the patients considered as potential candidates will be informed about the purpose of the study. Their positive response to the expression of interest will be followed by a new clinical evaluation to assess their current clinical status and obtain their base line for further evaluation.

An informed consent form will be signed prior to the clinical evaluation required for the participation to the study.

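### Section 4.2 has health-record information and eligibility questionnaires taken before the consent form is signed, against Sections 3.7.2, 3.4.2 and 4.3

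*Protocol*

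**What the plan says.** Section 3.7.2 describes recruitment from existing patient pools. Records are first screened on the last clinical evaluation. Patients who express interest then have "a new clinical evaluation to assess their current clinical status and obtain their base line for further evaluation". On consent the section says: "An informed consent form will be signed prior to the clinical evaluation required for the participation to the study".

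Section 4.2 describes the same stage step by step. For willing patients who meet the selection criteria, "complementary diagnostic exams will be held to validate in certainty that they do not meet exclusion criteria relating to recent illness". At the recruitment appointment the consent form is presented "but is not signed by him/her yet". Next, "personal health record information (presented in section 3) is collected and two important questionnaires are applied firstly", because the results can exclude the patient. After these have been analysed: "Once all the eligibility conditions are confirmed, the participant is considered recruited, and then is invited to sign the ICF". The signature sets the Recruitment day timestamp. At that point the "initial RETENTION patient record is about to created, while answers (values) of" the questionnaires are to be entered as well.

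Two other sections bear on the order. Section 3.4.2 includes written informed consent among the general inclusion criteria. Section 4.3 starts the baseline assessment, with its personal health-record parameters, once the signed form has been stored.

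**The concern.** Sections 3.7.2 and 4.2 put the same screening activity on opposite sides of consent. Section 4.2 is the operational text, so it is the one site staff are likely to follow. Under it, people give health information and answer questionnaires for the study before agreeing in writing to take part, and those found ineligible never sign at all. For those who enter, evidence of eligibility predates the consent date and is carried into the trial record.

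Section 3.2.3 commits the study to Good Clinical Practice and says the consent form will receive particular emphasis for data-protection compliance. A protocol with two incompatible consent points does not give an ethics committee or a monitor one rule to check against. Once patients have been screened in the wrong order, it cannot be put right afterwards.

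**Working it through.** No arithmetic applies. The check is a comparison of the order of steps.

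| Step | Section 3.7.2 | Section 4.2 | Section 4.3 |
|---|---|---|---|
| Screening of existing records | before consent | list formed beforehand (Section 4.1) | – |
| Exams to rule out exclusion criteria | part of the new evaluation, so after consent | apparently before consent (inferred) | – |
| Health-record information | after consent, if part of the new evaluation | before consent (explicit) | after consent (explicit) |
| Two eligibility questionnaires | after consent, if part of the new evaluation | before consent (explicit) | other questionnaires after consent |
| Eligibility confirmed | after consent | before consent (explicit) | – |
| Baseline assessment | after consent | after consent | after consent |

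1. *Health record and questionnaires.* Section 4.2 needs no interpretation here. The form is presented unsigned, the information is collected, the questionnaires are given and analysed, eligibility is confirmed, and signature follows.

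2. *Against Section 3.7.2.* That section describes one evaluation with two purposes, current clinical status and baseline, and says it is needed for participation. Consent precedes it. Section 4.2 splits the work and puts the eligibility part before consent.

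3. *Against Section 3.4.2.* Written consent is an inclusion criterion. Section 4.2 requires every eligibility condition to be confirmed before the patient is asked to sign. Both cannot hold.

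4. *Against Section 4.3.* Health-record parameters are collected there after the signed form is stored, while Section 4.2 collects health-record information before signature. The two adjoining sections disagree on this item.

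5. *The exams.* The exams sentence in Section 4.2 does not state its timing relative to signature. That they come first follows from their purpose, ruling out exclusion criteria, and from signature following confirmed eligibility. Section 4.1 also allows additional examinations during pre-recruitment, before the form has been presented.

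6. *The questionnaires.* Section 4.2 does not name them. The only inclusion criteria scored by questionnaire in Section 3.4.2 are the MoCA and the PHQ-9, so these are the likely pair, by inference.

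**The case against.** The strongest defence is that the evaluation in Section 3.7.2 means the baseline assessment, since it is said to yield the baseline. Sections 4.2 and 4.3 both start the baseline assessment after signature, and Section 3.7.2 itself lets existing records be screened earlier. On that reading much of the conflict goes. It does not all go. The evaluation in Section 3.7.2 also covers current clinical status and is needed for participation, and the conflicts with Sections 3.4.2 and 4.3 remain. Nor is this chart review: the questionnaires are newly given because their results can exclude the patient from this study.

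A second defence is that Section 4.2 calls recruitment a procedure with prior local ethics approval. Section 3.7.1 schedules those approvals for M20, while Section 3.3 has the protocol finalised at M13, so the phrase describes an intended state and does not settle which order was approved.

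Some of the defence stands:

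- Section 4.2 creates the patient record and identifier only after signature, so nothing shows data of screened-out patients entering the platform.
- The timing of the diagnostic exams is inferred. A reader might conclude that patients certainly undergo study exams without consent, but the text does not say so.
- A reader might infer that the PHQ-9 baseline for secondary endpoint k would be lost. Section 3.7.3 schedules the PHQ-9 at registration and allows 15 days either side of each visit, and Section 4.3 has questionnaires filled in after consent, so a post-consent baseline is possible.
- A reader might infer that data taken before consent would be thrown out on audit. Nothing in the protocol says that.

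**Conclusion.** The contradiction is real and Section 4.2 is wrong as written. It rests on explicit text for the health-record information, the two questionnaires and the confirmation of eligibility. It rests on inference for the diagnostic exams and for the identity of the questionnaires.

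The order in Section 4.2 applies to all 450 planned participants and to anyone who screens out at that appointment. A reader might want to put a number on the second group, but the protocol gives no screening failure rate. Patients are also checked against the criteria before they are called, which could make failures at that stage few. No figure is supportable.

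The point does not touch the primary endpoint, the significance level or the power. It concerns participant protection and a single, checkable consent date. It should be settled before the first patient is screened.

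**What to change.** Reorder Section 4.2 to match Section 3.7.2: information given; consent form signed; study-specific exams and questionnaires; eligibility confirmed; patient record created; randomisation. State which step the Recruitment day timestamp then marks, since Section 4.2 now ties it to a signature that comes last.

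Reconcile the related sections to the same consent point:

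- Section 3.4.2: written consent is obtained first and the remaining criteria are checked after it.
- Section 4.1: say whether any additional examinations are routine care or study-specific, and place study-specific ones after consent.
- Section 4.3: say which health-record items are collected at screening and which at baseline, both after consent.

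Screening of existing routine records may stay before consent, as Section 3.7.2 already allows. Name the two questionnaires.

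The change is to wording only and should need no additional visit or staff. The cost is some extra signed forms from patients who then prove ineligible.
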